4.6.1 Early Termination Study Visit

Subjects who withdraw from the study will be asked to notify the study team of their decision. If participants indicate that they do not want us to collect, use, or share their health information any longer, we will ask them to inform a research team member or the Principal Investigator, [name].

5 STUDY EVALUATIONS AND MEASUREMENTS

5.1 Screening and Monitoring Evaluations and Measurements

5.1.1 Medical Record Review: Screening

The CHOP/HUP/PAH electronic medical record (EMR) will be accessed to identify potential candidates who are CHOP/HUP/PAH patients. Screening for eligibility based on medical record review will include:

- Date of birth (inclusion criterion)
- Gender
- Gestational age (inclusion criterion)
- Race

- Ethnicity
- Moderate or severe BPD based on the NIH consensus definition at 36 weeks postmenstrual age (inclusion criterion)(12)
- Presence of any exclusion criteria

5.1.2 Inpatient Data Collection

After enrollment and randomization, the following data will be collected from the EMR while the patient is in the hospital:

- Birthweight
- Birth hospital
- Date of transfer to CHOP,HUP, of PAH (if applicable)
- Antenatal steroid treatment
- Reason for preterm birth
- Respiratory support
- Growth parameters at 36 weeks PMA
- Growth parameters at 40 weeks PMA
- Treatment with the following medications for BPD: iNO, postnatal steroids, inhaled bronchodilators, inhaled steroids, other
- Any surgeries
- Neonatal morbidities (surgical NEC, PDA ligation, ROP surgery, etc).
- Screening for pulmonary hypertension

5.1.3 Discharge Data Collection

- Discharge feeding plan
- Discharge respiratory support
- Discharge medications
- Discharge growth parameters
- Discharge date

5.1.4 Outpatient Data Collection

During the remainder of the study period, the following data will be collected:

- Rehospitalizations: location, duration, and ICU care, primary reason for hospitalization
- Medication use
- Visits to doctor or emergency room, with reason
- Procedures or surgeries
- Growth parameters as assessed at any clinical visit(s)
- Mode of feeding
- Developmental assessment (Bayley screener)

5.1.5 Parental Data Collection

- Infant quality of life questionnaires

5.2 Efficacy Evaluations

5.2.1 Efficacy Evaluations: Oximetry

This pilot trial is designed to assess the efficacy of continuous transmission of pulse oximetry from the home environment, for use in oxygen titration and monitoring for clinical care and research purposes. Therefore the study outcomes are designed to assess the efficacy of the study monitoring itself as well as the intervention of randomization to higher or lower oxygen saturation target ranges for infants with BPD.

For this study, we define intermittent hypoxemia as $\text{SpO}_2 < 80\%$ for > 30 seconds. In keeping with the prior literature, we will also report severe IH events, defined as $\text{SpO}_2 < 80\%$ for > 60 seconds. In the current study, we will utilize 2-second sampling and averaging times. IH will be measured longitudinally throughout the study period in all participants regardless of home oxygen use. IH will be reported as weekly average number of events per “night” based on 8 hours of recorded oximetry data per night. If data are not available for all nights in a week, the available data will be used to estimate average number of events per night for that week. Specific outcomes of interest are differences between the two groups in incidence of IH at 40 weeks PMA, 3 months CA, and 6 months CA. In addition, we will report percent of recording time spent $< 80\%$, $< 85\%$ and $< 90\%$ SpO_2 over the study period.

Duration of exposure to supplemental oxygen will be measured as the number of weeks between 36 weeks PMA (the time of formal diagnosis of BPD) and complete discontinuation of supplemental oxygen. This outcome is defined in weeks, not days, because this more closely matches the pace

with which changes are made in the outpatient setting. Prior studies demonstrated that it can be challenging, but nevertheless possible to keep infants in goal SpO₂ ranges during hospitalization. However, no studies have performed this maneuver after discharge. To demonstrate successful implementation of our study intervention and monitoring technology, percent of usable data and percent of time with SpO₂ in target range over time will be reported. Time with SpO₂ in the target range will be reported as a percent of oximeter recordings with SpO₂ in range, out of total recorded time. These outcomes are key components of demonstrating feasibility of the study intervention for future research and clinical use.

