Test Article(s)	
Preterm born infants who remain on respiratory support at 34-44 weeks PMA will be randomized to higher or lower oxygen saturation target ranges, which will be maintained until 6 months corrected age. Both of these target ranges are within the wider range commonly used in clinical practice.
 
 • For the lower target group our goal is to keep oxygen saturations between 90-94%. In hospital, inspired oxygen will be adjusted as needed to maintain target SpO_2. Monitoring will continue after discharge, and whenever children are discharged on supplemental oxygen, oxygen flow will be titrated monthly according to a standardized algorithm. • For the higher target group our goal is to keep oxygen saturations greater than or equal to 96%. In hospital, inspired oxygen will be adjusted as needed to maintain target SpO_2. Monitoring will continue after discharge, and whenever children are discharged on supplemental oxygen, oxygen flow will be titrated monthly according to a standardized algorithm.
Study Design	Randomized controlled pilot study.

Subject Population key criteria for Inclusion and Exclusion:	Inclusion Criteria 
 1. Pre-term male or female infants born at <30 0/7 weeks gestation 2. Current age 34 0/7 to 43 6/7 weeks postmenstrual age 3. Diagnosis of moderate or severe Bronchopulmonary Dysplasia based on the NIH consensus definition 4. Infant has never been discharged to home from the hospital Exclusion Criteria 
 1. Congenital anomaly or oncologic process likely to affect growth or respiratory status 2. Hemoglobinopathy or other blood disorder likely to affect oxygen saturations 3. Contraindication to nasal cannula use (for example, severe nasal septal breakdown) 4. Pulmonary hypertension requiring pharmacotherapy at the time of screening/enrollment 5. Tracheostomy 6. Intubated during entire eligibility period
Number Of Subjects	50 enrolled (42 evaluable) between CHOP, HUP, and PAH
Study Duration	Each subject's participation will last up to 8 months. The entire study is expected to last 3 years.
Study Phases	1) Baseline/Screening: screening for eligibility and obtaining consent
Screening	2) Phase 1: Inpatient
Study Treatment	3) Phase 2: Outpatient oxygen Saturation Monitoring (discharge to 6 months CA)
Follow-Up	4) Phase 3: Outcomes assessment at 3 and 6 Months CA

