3.1.3 Phase 2 – Outpatient monitoring

At the time of hospital discharge, as detailed below, families will be given a Masimo oximeter along with a device that will transmit the oximetry data back to the study team at CHOP. They will be instructed how to use the device nightly while the child is sleeping at home.

Infants who are discharged per clinical recommendations on supplemental oxygen will have frequent visits in the CHOP Pulmonary Clinic. Oxygen titration and weaning will be standardized according to the algorithm in Table 2, below.

Table 2: Home Nasal Cannula Flow Titration Algorithm*		
	HIGHER SpO₂ TARGET ARM ($\geq 96\%$)	LOWER SpO₂ TARGET ARM ($\geq 90\%$)
Criteria for INCREASING O ₂ flow rate	SpO₂ < 96% for > 10% of recorded time	SpO₂ < 90% for > 10% of recorded time
Criteria for MAINTAINING current O ₂ flow rate	SpO₂ $\geq 96\%$ for 90-95% of recorded time	SpO₂ > 90% for $\geq 90\%$ of recorded time but NOT > 94% for $\geq 90\%$ of recorded time
Criteria for WEANING O ₂ flow rate	SpO₂ $\geq 96\%$ for >95% of recorded time	SpO₂ > 94% for $\geq 90\%$ of recorded time

*Decisions will be made by assessment of recorded oximetry. A minimum of 4 days of data, with a minimum of 8 hours per day, will be required for analysis to make a wean. Oxygen flow rates will be decreased stepwise: 2 LPM – 1.5 LPM – 1 LPM – 1/2 LPM – 1/4 LPM – 1/8 LPM. Once the child is stable on 1/8 LPM, he/she will be weaned off for increasing duration of time: first 6 hours, then 12 hours per day, and finally off completely.

Downloaded oximetry data will be reviewed and decisions about weaning will be made each week by the study team (including [name] from the Division of Pediatric Pulmonology). In the home setting, weans may be performed as often as every week. If an infant loses >5% of body weight in any month, no oxygen weans will be made until the weight is regained. If an infant is discharged without oxygen or weans off but then meets the criteria for increasing flow on two subsequent recordings, the family will be instructed to attend pulmonary clinic for assessment and then home oxygen therapy will be instituted.

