3.1.4 Phase 3 – 3 and 6 month corrected age outcomes assessment

Per standard of care, participants will be evaluated in the CHOP Neonatal Follow-up Program at 3 and 6 months corrected ages. Several study outcomes, clinical outcomes in particular, will be assessed during these clinical visits. Based on the limited existing literature, average age of weaning from supplemental oxygen in infants with BPD is between 2-4.5 months corrected age.(9,10) For the current study, the oxygen titration protocol and study oximetry will continue until 6 months corrected age, with the expectation that nearly all participants will have weaned to room air by the end of the study period. If participants remain on oxygen after the conclusion of the study, the pediatric pulmonologist primarily responsible for the child's ongoing BPD care will make decisions about further weaning. For all other participants, ongoing clinical care will be provided by the neonatal follow-up clinic and pediatrician.

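### Percent time in target range counts room-air recordings, so it cannot isolate oxygen targeting or be compared between the arms

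*Combined protocol and SAP*

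**What the plan says.** Section 5.2.1 gives the measure its purpose, "To demonstrate successful implementation of our study intervention and monitoring technology", and calls it a key part of showing feasibility for later research and clinical use. It is to be shown over time, and it "will be reported as a percent of oximeter recordings with SpO₂ in range, out of total recorded time". Nothing restricts it to time on oxygen.

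The same section states that "IH will be measured longitudinally throughout the study period in all participants regardless of home oxygen use". Section 3.1.4 puts average weaning at 2 to 4.5 months corrected age (CA) and continues oximetry to 6 months CA, "with the expectation that nearly all participants will have weaned to room air by the end of the study period". Section 3.1.3 also allows for infants who go home without oxygen.

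On the ranges, the synopsis says "For the lower target group our goal is to keep oxygen saturations between 90-94" (percent), and the abstract and section 7.1 agree. The higher arm is 96% or more. At home, Table 2 in section 3.1.3 governs flow for infants on oxygen. For an infant in room air the only oxygen action is to start it, when the infant goes home without it or "weans off but then meets the criteria for increasing flow on two subsequent recordings".

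**The concern.** An implementation measure should move when targeting gets better or worse. This one also moves when infants come off oxygen, and in opposite directions in the two arms. A healthy infant in room air counts as a success if assigned to the higher range and as a failure if assigned to 90-94%, although nobody is targeting anything in either case.

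The pilot is meant to inform a later trial. With the measure as defined, a low figure in the lower arm could be taken to show that 90-94% cannot be achieved at home, when it may only show that the infants weaned. A high figure in the higher arm could be taken as good titration, when it may partly reflect infants who needed no oxygen.

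**Working it through.** The protocol states no expected value for time in range, so there is no figure to reproduce.

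**Step 1: one room-air recording, from the definitions alone.** Take an 8-hour night in room air with SpO2 at 96% or more for over 95% of the time.

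- Higher arm: in range for more than 0.95 × 8 = 7.6 h, that is, above 95%.
- Lower arm (90-94%): less than 8 − 7.6 = 0.4 h remains for all values under 96%, so below 5% is in range.

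This step needs no outside assumption.

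**Step 2: how room air enters a summary.** Let r be the room-air share of recorded time, p the percent in range on oxygen (equal in both arms, meaning equally good targeting), a the room-air share of time at 96% or more in the higher arm, and b the room-air share at 90-94% in the lower arm.

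- Higher arm = (1 − r) × p + r × a
- Lower arm = (1 − r) × p + r × b
- Gap = r × (a − b), which does not depend on p

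The formula holds for a total over follow-up and equally for one calendar week, with r as that week's room-air share. A display over time therefore shows the mixing change as infants wean but does not undo it.

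**Step 3: plausible values of r.** With weaning at 4.5 or 2 months CA (section 3.1.4):

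- Even recording from term to 6 months CA (assumed): (6 − 4.5)/6 = 25% and (6 − 2)/6 = 67%.
- With 4 weeks of continuous inpatient recording before term and 8 h per night afterwards (assumed; 30.4375 days per month): total = 28 × 24 + 6 × 30.4375 × 8 = 672 + 1461 = 2133 h. Room air is 1.5 × 30.4375 × 8 = 365 h (17%) or 4 × 30.4375 × 8 = 974 h (46%).

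Early stopping at parental request after 8 room-air weeks without intermittent hypoxemia (section 4.3.3) would lower r further, for reasons unrelated to targeting.

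**Step 4: gap in percentage points.** The values of a and b are assumptions.

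| a, b | r = 17% | r = 25% | r = 46% | r = 67% |
|---|---|---|---|---|
| 90%, 4% | 15 | 22 | 39 | 57 |
| 75%, 12% | 11 | 16 | 29 | 42 |
| 60%, 20% | 7 | 10 | 18 | 27 |

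Example with p = 70%, r = 25%, a = 75%, b = 12%: higher arm 0.75 × 70 + 0.25 × 75 = 71.3%; lower arm 0.75 × 70 + 0.25 × 12 = 55.5%. Restricted to time on oxygen (r = 0), both arms read 70%.

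The table uses the same weaning age in both arms. Any recording that meets the higher arm's wean row in Table 2 also meets the lower arm's, so the lower arm may spend more time in room air. In that case r differs by arm and the gap no longer reduces to this formula.

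**The case against.** The plan has a fair defense. The measure is descriptive, no decision threshold uses it, and no test between arms is specified for it. It is to be shown over time, beside the number of weeks on oxygen, so a reader would see some of the drift. All-time SpO2 by arm is also a legitimate description of what each assigned strategy delivered. All of this stands, and it limits the weight of the point. It does not remove it: infants wean at different ages, so any given week mixes the two states, and the stated purpose is to demonstrate implementation.

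Three stronger readings are tempting, and the protocol does not support them.

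- That the measure says nothing about targeting. Inpatient recordings and home recordings on oxygen do carry that information.
- That low scores on recordings that trigger a wean are an artefact. The lower-arm wean row requires SpO2 above 94% for at least 90% of the time, so at most 10% is in range. But an infant on oxygen at that level really is above 90-94%, and the low score is correct.
- That the lower arm has two competing targets because the Table 2 column head reads 90% or more. The maintain and wean rows under that head use 94% as an upper limit, and the abstract, synopsis and section 7.1 all give 90-94%. The head is best read as a titration floor. What remains is that section 5.2.1 does not restate the reporting range.

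**Conclusion.** The point holds as a fault in how a feasibility measure is defined. Out of total recorded time, percent time in range cannot isolate oxygen targeting and should not be compared between the arms. Step 1 is certain from the definitions: the same good room-air night scores above 95% in one arm and below 5% in the other.

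The overall size is not known. The 7 to 57 points above rest on assumed recording patterns, assumed room-air SpO2 and equal weaning ages, and the top of the range also requires a single figure over all follow-up, which the plan does not call for. The range shows that the effect need not be small; it is not an estimate.

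A reader might infer that the trial's main comparison is compromised. It is not. Intermittent hypoxemia and time below 80%, 85% and 90% use the same thresholds in both arms, and the sample size does not depend on this measure. What is at stake is the conclusion about whether home targeting is feasible.

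**What to change.** In section 5.2.1:

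- State that the lower range for reporting is 90-94%, and tidy the Table 2 column head to match.
- Report by arm the percent of recorded time below, in and above range (no above-range entry in the higher arm), separately for home time with prescribed oxygen, home time in room air, and inpatient time.
- Base the home implementation statement on the prescribed-oxygen time.
- For room-air time, show percent below the arm's lower limit (90% or 96%), since starting oxygen is the only oxygen action the algorithm provides there.
- Say in advance where weeks of part-day weaning (footnote to Table 2) are counted.
- Keep the all-time figure as a description of delivered SpO2, and do not test the arms against each other.

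Targets, titration rules, visits and sample size stay as they are. Much of the oxygen status is already available: respiratory support in hospital and at discharge (sections 5.1.2 and 5.1.3), the weekly weaning decisions (sections 3.1.3 and 4.3.1) and the week oxygen stops (section 5.2.1). The outpatient list in section 5.1.4 has no flow item, so one simple weekly oxygen-status field may be needed.

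There is a price. Time on oxygen is a post-randomization subset that shrinks as infants wean and leaves the sicker ones, and infants never on home oxygen contribute nothing to it. The report should say so and show the number of infants behind each row.

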5.2.2 Efficacy Evaluations: Clinical

In this pilot study, physiologic (oximetry) data are the primary outcomes. All clinical outcomes/assessments of efficacy are exploratory and descriptive. Methods and timing of measures that will be used to assess efficacy are:

Primary Clinical Outcome:

Growth in kilograms between 36 weeks PMA and 6 months CA as well as other growth parameters.

- Change in Length (cm)
- Weight for length
- Head circumference (cm)

Secondary Clinical Outcomes:

- Feeding questionnaire: The questions that will be asked at 3 and 6 months are selected to assess feeding skills and estimate caloric intake. The questions are selected from longer questionnaires administered as part of the Millennium Birth Study, with permission from the author of the original study.(13)
- The ITQOL---SF47- Parent and child quality of life survey: The Infant Toddler Quality of Life Questionnaire™ (ITQOL) was developed for use in infants and toddlers at least 2 months of age up to 5 years. The Infant Toddler Quality of Life Questionnaire™ (ITQOL) adopts the World Health Organization's definition of health, as a state of complete physical, mental and social wellbeing and not merely the absence of disease. The survey was developed following a thorough review of the infant health literature and a review of developmental guidelines used by pediatricians. The ITQOL includes questions that assess the impact of health on both child and parent quality of life.
- Medical resource utilization recorded at 3 and 6 months corrected age: medications (including dose, route, frequency, and indication), doctor and emergency room visits, hospitalizations (whether or not in ICU, duration, and indication), therapies (type and frequency), and home equipment use. These data will be extracted from the EMR wherever possible and verified with the participant's parent(s).
- Development: Per standard of clinical care, the Bayley Scales of Infant Development- 3rd Edition Screening Test is administered to all children who attend the Neonatal Follow-up Program (NFP) at 6 months corrected age. (All children eligible for this study will be

followed at the NFP per standard of care) Results of this clinical evaluation will be recorded for the study.

5.3 Safety Evaluation

Subject safety will be monitored by adverse events, as well as the clinical outcomes as described above. Potential adverse clinical outcomes based on the prior literature are pneumonia/BPD exacerbations and detrimental effects on parental quality of life.

6 STATISTICAL CONSIDERATIONS

6.1 Primary Endpoint

The primary endpoints are the incidence of intermittent hypoxemia (IH, SpO₂ <80% for >=30 seconds) and total duration of hypoxia up to 6 months corrected age among infants with BPD randomized to higher versus lower SpO₂ target ranges.

6.2 Secondary Endpoints

All secondary endpoints in this pilot study are essentially exploratory and descriptive. The primary clinical outcome is growth in kilograms between 36 weeks PMA and 6 months CA. In addition, the study will also report:

- The change in other growth parameters - length (cm), weight for length, and head circumference (cm) - between 36 weeks PMA and 40 weeks PMA, 3 months CA, and 6 months CA.
- Differences between groups on a standardized feeding questionnaire at 3 and 6 months CA.
- Differences between groups in parent and child quality of life at 3 and 6 months CA.
- Differences between the groups in health care utilization at 3 and 6 months CA.
- Differences between the groups in development at 6 months CA.
- Safety, assessed as differences in growth, re-hospitalizations, and any safety events at 3 and 6 months CA.

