The PI will be responsible for monitoring the data and safety of all participants. All study procedures will receive IRB approval prior to recruitment or enrollment of participants. In addition to the data management procedures outlined above, the PI will hold monthly study team meetings to evaluate the safety and progress of all research procedures. Standard procedures for all data collection methods will be reviewed at the start and periodically throughout the study. Data checks for errors will be performed prior to analysis. Adverse events and serious adverse events will be reported to the

TABLE 1: SCHEDULE OF STUDY PROCEDURES

Study Activity	Recruitment Phase & Screening	Enrollment Phase	Study Timeframe					
			Baseline 34-44 (weeks)	Discharge	Weekly after discharge	Monthly after discharge	3 Months CA	6 Months CA
Pre-Enrollment Pool EPIC-CHOP/PENN/PAH	X							
Medical Record Review	X							
Conduct Eligibility Screen	X							
Approach Families (Beginning 34weeks, PMA)		X						
Parental Consent			X					
Participant Randomization			X					
Weight, length, and head circumference are measured			X				X	X
Placement of SPO2 study monitors/ training with families					Continuous over 6 months			
Feeding questionnaire and diary							X	X
Data from monitor are reviewed by study team and family is contacted if needed					Weekly data transfers to CHOP			
Feeding Questionnaire**							X	X
ITQOL-SF47 (Parent/Child quality of life) **							X	X
Health care utilization data is collected							X	X
Bayley Scales of Infant Development Screener								X
Participant Compensation. Payments issued monthly(\$50/visit; up to 6 visits)						X		

Adverse Event/Serious Adverse Event Assessment			X	X	X		X	X
--	--	--	---	---	---	--	---	---

FIGURE 1: SCHEMATIC OF STUDY PROCEDURES

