3.1.1 Screening- Baseline

Potential subjects will be screened using the protocol inclusion and exclusion criteria. Parental/guardian permission (informed consent), will be obtained prior to any study related procedures being performed. Randomization occurs when infants have been extubated. However, parents of infants who are on higher levels of support, may be approached to introduce the study. Consent will be obtained at time of extubation. Once the infant meets all eligibility criteria (, the

subject will be randomized to higher or lower oxygen saturation (SpO₂) target ranges and study monitoring (3.1.2) will begin.

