3.1.2 Phase 1 – Inpatient monitoring

After randomization, the alarm settings on the standard hospital equipment will be adjusted according to the participant's group assignment. The study SpO₂ ranges are similar to the standard of care ranges in the CHOP NICU, where the clinical alarms for infants born <30 weeks are 95% (high) and 87% (low) until 36 weeks PMA. After 36 weeks PMA, alarms are set at 98% (high) and 90% (low). Participants will continue on the study-mandated alarm settings until discharge to home.

In addition, participants will be placed on the study monitor in order to facilitate collection of study data. This is similar to the approach previously used in the CHOP and HUP NICUs for the Canadian Oxygen Trial. Nurses will be instructed to follow alarms from the clinical monitors, not the study monitor, while the infant is in the NICU. Per standard of care, the infant will be on the clinical monitor continuously. Every effort will be made to also keep the infant on the study monitor continuously; however, it is sufficient to have minimum of 4 days per week/8 hours per day of data. This is consistent with the minimum planned data collection planned for the outpatient phase of the study.

If patients are reintubated, oxygen saturation targets will be at the discretion of the clinical team. However, they will be encouraged to maintain the study mandated targets.

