3.4.1 Inclusion Criteria

- 1) Patient at CHOP,HUP, PAH (including both inborn and outborn infants)
- 2) Pre-term males or females infants born at <30 0/7 weeks gestation
- 3) Current age 34 0/7 to 43 6/7 weeks postmenstrual age
- 4) Diagnosis of moderate or severe Bronchopulmonary Dysplasia (as above)
- 5) Infant has never been discharged to home from the hospital

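### Growth is counted from 36 weeks PMA although randomisation may come as late as 43 6/7 weeks; comparing 6-month size adjusted for size and age at randomisation would remove avoidable noise

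*Combined protocol and SAP*

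**What the plan says.** Section 6.2 states: "The primary clinical outcome is growth in kilograms between 36 weeks PMA and 6 months CA". Section 5.2.2 and the synopsis define the outcome the same way. Section 6.2 also reports change in length, weight for length and head circumference "between 36 weeks PMA and 40 weeks PMA, 3 months CA, and 6 months CA".

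Entry is not tied to 36 weeks. Section 3.4.1 requires "Current age 34 0/7 to 43 6/7 weeks postmenstrual age". Section 3.1.1 adds: "Randomization occurs when infants have been extubated". The assigned target takes effect later still, under section 3.1.2: "After randomization, the alarm settings on the standard hospital equipment will be adjusted according to the participant's group assignment".

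Table 1 has a row reading "Weight, length, and head circumference are measured", marked in the 34-44 week baseline column and at 3 and 6 months CA. No growth outcome refers to that baseline value. The candidate covariates in section 6.3.2 are gender, gestational age, birth weight, race, small size for gestational age and BPD severity. They enter a model only if they differ significantly between arms. Weight and PMA at randomisation are not among them.

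Section 5.2.1 likewise counts oxygen exposure from a fixed age, as "the number of weeks between 36 weeks PMA (the time of formal diagnosis of BPD) and complete discontinuation of supplemental oxygen".

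**The concern.** The SpO₂ target cannot affect growth that happened before it was assigned. For infants randomised after 36 weeks, the growth outcome adds a stretch of unassigned growth to the stretch under the target. That earlier stretch brings infant-to-infant variation unrelated to treatment, and in a sample of 42 it can fall unevenly between arms by chance.

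Growth is the only clinical outcome with a power statement (section 6.4), and section 6.3.2 says the exploratory analyses should help plan later studies. An SD larger than it need be would carry into that planning. The short windows are the most exposed: a 36-to-40-week change can lie wholly before randomisation and still be reported by arm.

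**Working it through.** **Inputs.** From the documents: growth from 36 weeks PMA to 6 months CA (6.2); entry up to 43 6/7 weeks (3.4.1); mean weights of 2.8 kg and 7.9 kg, a target difference of 0.5 kg and 42 children (6.4). Assumed: term is 40 weeks, 6 months is 26.09 weeks, 21 infants per arm.

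**The plan's own figures.** Mean gain is 7.9 − 2.8 = 5.1 kg, as stated. The claim of more than 80% power for 0.5 kg cannot be reproduced, because no SD, alpha or sidedness is given. With two-sided 5% and a normal approximation, it needs an SD of at most 0.5 / [(1.960 + 0.842) × √(2/21)] = 0.5 / (2.802 × 0.3086) = 0.578 kg.

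**Share of the interval before the target.**
- The interval is 40 + 26.09 − 36 = 30.09 weeks.
- The latest entry is 43.86 − 36 = 7.86 weeks into it, and 7.86 / 30.09 = 26.1%.
- Entry at 38, 40 or 42 weeks gives 2, 4 or 6 weeks out of 30.09: 6.6%, 13.3% or 19.9%. Entry by 36 weeks gives 0%.
- The window to 3 months CA is 40 + 13.04 − 36 = 17.04 weeks, so the worst case is 7.86 / 17.04 = 46.1%.
- In the 36-to-40-week window, entry at 40 weeks or later gives 4 / 4 = 100%.

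**What this does to the comparison of arms.** The mean rate of gain is 5.1 / 30.09 = 0.1695 kg per week, taken as linear. Mean gain before randomisation is then 0.1695 × 7.86 = 1.33 kg at the latest entry. If entry is uniform over 36 to 43 6/7 weeks, it averages 0.1695 × 3.93 = 0.67 kg. Both arms carry this mean, so it cancels. What remains is the infant-to-infant deviation, with SD = 0.1695 × CV × √E(D²), where D is weeks from 36 weeks to randomisation and CV is the coefficient of variation of weekly gain. Under uniform entry E(D²) = 7.857² / 3 = 20.58, with root 4.54.
- CV 15%: SD 0.115 kg; standard error of the arm difference 0.115 × 0.3086 = 0.04 kg.
- CV 30%: SD 0.231 kg; standard error 0.231 × 0.3086 = 0.07 kg.

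**Precision available from adjustment.** This is an illustrative simulation with 400,000 infants per setting and a 36-week weight SD of 0.35 kg. It compares the SD of change since 36 weeks with the residual SD of 6-month weight after adjustment for weight and PMA at randomisation. All variance and entry inputs are assumptions.

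| Entry | CV before / after | Correlation | SD of change (kg) | Adjusted SD (kg) | Reduction |
|---|---|---|---|---|---|
| Uniform | 15% / 10% | 0 | 0.459 | 0.445 | 3% |
| Uniform | 30% / 10% | 0.5 | 0.579 | 0.433 | 25% |
| Uniform | 10% / 10% | 0 | 0.453 | 0.446 | 1.5% |
| Uniform | 20% / 20% | 0.5 | 0.965 | 0.880 | 9% |
| Near 36 weeks* | 10% / 10% | 0 | 0.486 | 0.485 | 0.3% |
| Near 36 weeks* | 20% / 20% | 0.5 | 0.997 | 0.969 | 3% |

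*Exponential delay, mean 1.5 weeks.

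Adjusting 6-month weight for 36-week weight alone left the SD the same as that of the raw change in every setting. In this model the gain comes from using the measurement at randomisation.

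**Oxygen duration.** Let S be age at stopping oxygen, E age at entry, and b the slope of S on E. Then Var(S − E) = Var(S) + Var(E)(1 − 2b), so counting from randomisation lowers the variance only if b exceeds 0.5. The documents do not give b. Under uniform entry the SD of E is 7.857 / √12 = 2.27 weeks, so the subtraction brings in a chance imbalance with standard error 2.27 × 0.3086 = 0.70 weeks.

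**The case against.** The strongest defence is that a fixed age interval is a coherent choice. Every infant contributes the same 36-weeks-to-6-months span whenever randomised, so unequal entry age does not become unequal growth, and randomisation balances the earlier part. That stands. It rules out a claim of bias and rules out raw change since randomisation as a substitute, because that interval would vary between infants. It does not remove the added variance.

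Three stronger readings are tempting, and the documents support none of them.
- A reader might set the 0.67 to 1.33 kg of earlier gain against the 0.5 kg target difference. That gain is a level common to both arms. The relevant quantity is its chance imbalance, about 0.04 to 0.07 kg under the assumptions above.
- A reader might infer that the 36-week anchor dilutes the treatment effect and costs power. Shorter exposure in late entrants comes from the eligibility window. The expected arm difference in 6-month weight is the same under either anchor, so changing the anchor restores no lost effect.
- A reader might want oxygen duration counted from randomisation too. From a fixed age, the arm difference is simply the difference in mean age at stopping oxygen. Subtracting a varying entry age may add noise, and section 5.2.1 gives a reason for the 36-week start.

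Two further points stand. Sections 5.2.2 and 6.2 call the clinical outcomes exploratory and descriptive, which limits the stakes. It is also not certain that Table 1's baseline measurement falls at randomisation: its column spans 34-44 weeks, and section 5.1.2 lists growth at 36 and 40 weeks only.

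**Conclusion.** The point holds as one of precision. For a late entrant up to 26% of the growth interval precedes the assigned target; this is a share of time and the worst case for one infant. The average share is unknown, because the documents give no distribution of age at randomisation. For infants randomised after 40 weeks, the 36-to-40-week changes carry no information about the target.

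Adjusting 6-month size for size and PMA at randomisation would lower the outcome SD by somewhere between 0.3% and 25%. The top of that range needs weekly gain three times as variable before randomisation as after, a correlation of 0.5 between the two, and entry spread evenly to 43 6/7 weeks. With equal variability the reduction is about 1.5% to 9% under uniform entry and 0.3% to 3% if entry clusters near 36 weeks. There is no systematic bias, and the case does not extend to oxygen duration. The change is worth making because it is cheap, not because the present outcome is invalid.

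**What to change.** - In 5.2.2, 6.2 and 6.3.2, define the growth comparison as weight (and likewise length and head circumference) at 6 months CA between arms. Prespecify adjustment for the same measure at randomisation and for PMA at randomisation, whether or not these differ between arms at baseline.
- State in Table 1 and section 5.1.2 that the baseline measurement is the one taken at randomisation or nearest before it. This also covers any infant randomised before 36 weeks, whose 36-week weight would already be a post-randomisation value. The age window permits such entry, while Table 3 defines BPD by support at 36 weeks, so those passages should be reconciled.
- Keep gain since 36 weeks as a descriptive figure. Do not interpret the 36-to-40-week change as a treatment effect for infants randomised after 40 weeks.
- Leave oxygen duration counted from 36 weeks PMA. At most, report weeks on oxygen before randomisation as a baseline characteristic.

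The cost is wording, a clear date for a measurement that Table 1 appears to schedule already, and two covariates in a model with 42 infants.
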